11.2.3 Methods for Evaluation of Measurable Disease

All measurements should be taken and recorded in metric notation using a ruler or calipers. All baseline evaluations should be performed as closely as possible to the beginning of treatment and never more than 4 weeks before the beginning of the treatment.

The same method of assessment and the same technique should be used to characterize each identified and reported lesion at baseline and during follow-up. Imaging-based evaluation is preferred to evaluation by clinical examination unless the lesion(s) being followed cannot be imaged but are assessable by clinical exam.

Clinical lesions: Clinical lesions will only be considered measurable when they are superficial (e.g., skin nodules and palpable lymph nodes) and $\geq 10 \text{ mm}$ ($\geq 1 \text{ cm}$) diameter as assessed using calipers (*e.g.*, skin nodules). In the case of skin lesions, documentation by color photography, including a ruler to estimate the size of the lesion, is recommended.

Chest x-ray: Lesions on chest x-ray are acceptable as measurable lesions when they are clearly defined and surrounded by aerated lung. However, CT is preferable.

Conventional CT and MRI: This guideline has defined measurability of lesions on CT scan based on the assumption that CT slice thickness is 5 mm (0.5 cm) or less. If CT scans have slice thickness greater than 5 mm (0.5 cm), the minimum size for a measurable lesion should be twice the slice thickness. MRI is also acceptable in certain situations (e.g., for body scans).

Use of MRI remains a complex issue. MRI has excellent contrast, spatial, and temporal resolution; however, there are many image acquisition variables involved in MRI, which greatly impact image quality, lesion conspicuity, and measurement. Furthermore, the availability of MRI is variable globally. As with CT, if an MRI is performed, the technical specifications of the scanning sequences used should be optimized for the evaluation of the type and site of disease. Furthermore, as with CT, the modality used at follow-up should be the same as was used at baseline and the lesions should be measured/assessed on the same pulse sequence. It is beyond the scope of the RECIST guidelines to prescribe specific MRI pulse sequence parameters for all scanners, body parts, and diseases. Ideally, the same type of scanner should be used and the image acquisition protocol should be followed as closely as possible to prior scans. Body scans should be performed with breath-hold scanning techniques, if possible.

PET-CT: At present, the low dose or attenuation correction CT portion of a combined PET-CT is not always of optimal diagnostic CT quality for use with RECIST measurements. However, if the site can document that the CT performed as part of a PET-CT is of identical diagnostic quality to a diagnostic CT (with IV and oral contrast), then the CT portion of the PET-CT can be used for RECIST measurements and can be used interchangeably with conventional CT in accurately measuring cancer lesions over time. Note, however, that the PET portion of the CT introduces additional data which may bias an investigator if it is not routinely or serially performed.

Ultrasound: Ultrasound is not useful in assessment of lesion size and should not be used as a method of measurement. Ultrasound examinations cannot be reproduced in their entirety for independent review at a later date and, because they are operator dependent, it cannot be guaranteed that the same technique and measurements will be taken from one assessment to the next. If new lesions are identified by ultrasound in the course of the study, confirmation by CT or MRI is advised. If there is concern about radiation exposure at CT, MRI may be used instead of CT in selected instances.

Endoscopy, Laparoscopy: The utilization of these techniques for objective tumor evaluation is not advised. However, such techniques may be useful to confirm complete pathological response when biopsies are obtained or to determine relapse in trials where recurrence following complete response (CR) or surgical resection is an endpoint.

Tumor markers: Tumor markers alone cannot be used to assess response. If markers are initially above the upper normal limit, they must normalize for a patient to be considered in complete clinical response. Specific guidelines for both CA-125 response (in recurrent ovarian cancer) and PSA response (in recurrent prostate cancer) have been published [*JNCI* 96:487-488, 2004; *J Clin Oncol* 17, 3461-3467, 1999; *J Clin Oncol* 26:1148-1159, 2008]. In addition, the Gynecologic Cancer Intergroup has developed CA-125 progression criteria which are to be integrated with objective tumor assessment for use in first-line trials in ovarian cancer [*JNCI* 92:1534-1535, 2000].

Cytology, Histology: These techniques can be used to differentiate between partial responses (PR) and complete responses (CR) in rare cases (*e.g.*, residual lesions in tumor types, such as germ cell tumors, where known residual benign tumors can remain).

The cytological confirmation of the neoplastic origin of any effusion that appears or worsens during treatment when the measurable tumor has met criteria for response or stable disease is mandatory to differentiate between response or stable disease (an effusion may be a side effect of the treatment) and progressive disease.

FDG-PET: While FDG-PET response assessments need additional study, it is sometimes reasonable to incorporate the use of FDG-PET scanning to complement CT scanning in assessment of progression (particularly possible 'new' disease). New lesions on the basis of FDG-PET imaging can be identified according to the following algorithm:

- a. Negative FDG-PET at baseline, with a positive FDG-PET at follow-up is a sign of PD based on a new lesion.
- b. No FDG-PET at baseline and a positive FDG-PET at follow-up: If the positive FDG-PET at follow-up corresponds to a new site of disease confirmed by CT, this is PD. If the positive FDG-PET at follow-up is not confirmed as a new site of disease on CT, additional follow-up CT scans are needed to determine if there is truly progression occurring at that site (if so, the date of PD will be the date of the initial abnormal

FDG-PET scan). If the positive FDG-PET at follow-up corresponds to a pre-existing site of disease on CT that is not progressing on the basis of the anatomic images, this is not PD.

c. FDG-PET may be used to upgrade a response to a CR in a manner similar to a biopsy in cases where a residual radiographic abnormality is thought to represent fibrosis or scarring. The use of FDG-PET in this circumstance should be prospectively described in the protocol and supported by disease-specific medical literature for the indication. However, it must be acknowledged that both approaches may lead to false positive CR due to limitations of FDG-PET and biopsy resolution/sensitivity.

Note: A 'positive' FDG-PET scan lesion means one which is FDG avid with an uptake greater than twice that of the surrounding tissue on the attenuation corrected image.

11.2.4 Response Criteria

11.2.4.1 Evaluation of Target Lesions

Complete Response (CR): Disappearance of all target lesions. Any pathological lymph nodes (whether target or non-target) must have reduction in short axis to <10 mm (<1 cm).

Partial Response (PR): At least a 30% decrease in the sum of the diameters of target lesions, taking as reference the baseline sum diameters.

Progressive Disease (PD): At least a 20% increase in the sum of the diameters of target lesions, taking as reference the smallest sum on study (this includes the baseline sum if that is the smallest on study). In addition to the relative increase of 20%, the sum must also demonstrate an absolute increase of at least 5 mm (0.5 cm). (Note: the appearance of one or more new lesions is also considered progressions).

Stable Disease (SD): Neither sufficient shrinkage to qualify for PR nor sufficient increase to qualify for PD, taking as reference the smallest sum diameters while on study.

11.2.4.2 Evaluation of Non-Target Lesions

Complete Response (CR): Disappearance of all non-target lesions and normalization of tumor marker level. All lymph nodes must be non-pathological in size (<10 mm [<1 cm] short axis).

Note: If tumor markers are initially above the upper normal limit, they must normalize for a patient to be considered in complete clinical response.

Non-CR/Non-PD: Persistence of one or more non-target lesion(s) and/or maintenance of tumor marker level above the normal limits.

Progressive Disease (PD): Appearance of one or more new lesions and/or unequivocal progression of existing non-target lesions. Unequivocal progression should not normally trump target lesion status. It must be representative of overall disease status change, not a single lesion increase.

Although a clear progression of "non-target" lesions only is exceptional, the opinion of the treating physician should prevail in such circumstances, and the progression status should be confirmed at a later time by the review panel (or Principal Investigator).

11.2.4.3 Evaluation of Best Overall Response

The best overall response is the best response recorded from the start of the treatment until disease progression/recurrence (taking as reference for progressive disease the smallest measurements recorded since the treatment started). The patient's best response assignment will depend on the achievement of both measurement and confirmation criteria.

| Target Lesions | Non-Target Lesions | New Lesions | Overall Response | Best Overall Response when Confirmation is Required* | | |
|-------------------|-----------------------|-------------|---------------------|---|--|--|
| CR | CR | No | CR | >4 wks. Confirmation** | | |
| CR | Non-CR/Non-PD | No | PR | | | |
| CR | Not evaluated | No | PR | >1 when Confirmation** | | |
| PR | Non-CR/Non- | No | PR | \geq 4 wks. Confirmation** | | |
| | PD/not evaluated | | | | | |
| SD | Non-CR/Non- | No | SD | Documented at least once ≥ 4 wks. | | |
| | PD/not evaluated | | | from baseline** | | |
| PD | Any | Yes or No | PD | | | |
| Any | PD*** | Yes or No | PD | no prior SD, PR or CR | | |
| Any | Any | Yes | PD | | | |
| * See RECIS | | | | | | |

For Patients with Measurable Disease (*i.e.*, Target Disease)

** Only for non-randomized trials with response as primary endpoint.

*** In exceptional circumstances, unequivocal progression in non-target lesions may be accepted as disease progression.

Note: Patients with a global deterioration of health status requiring discontinuation of treatment without objective evidence of disease progression at that time should be reported as "symptomatic deterioration." Every effort should be made to document the objective progression even after discontinuation of treatment.

For Patients with Non-Measurable Disease (i.e., Non-Target Disease)

| Non-Target Lesions | New Lesions | Overall Response |
|--------------------|-------------|------------------|
| CR | No | CR |
| Non-CR/non-PD | No | Non-CR/non-PD* |
| Not all evaluated | No | not evaluated |
| Unequivocal PD | Yes or No | PD |
| Any | Yes | PD |

'Non-CR/non-PD' is preferred over 'stable disease' for non-target disease since SD is increasingly used as an endpoint for assessment of efficacy in some trials so to assign this category when no lesions can be measured is not advised

11.2.5 Duration of Response

Duration of overall response: The duration of overall response is measured from the time measurement criteria are met for CR or PR (whichever is first recorded) until the first date that recurrent or progressive disease is objectively documented (taking as reference for progressive disease the smallest measurements recorded since the treatment started).

The duration of overall CR is measured from the time measurement criteria are first met for CR until the first date that progressive disease is objectively documented.

Duration of stable disease: Stable disease is measured from the start of the treatment until the criteria for progression are met, taking as reference the smallest measurements recorded since the treatment started, including the baseline measurements.

11.3 Lymphomas

- 11.3.1 Complete response (CR): Disappearance of all signs and symptoms of lymphoma for a period of at least one month. All lymph nodes and nodal masses must have regressed to normal size (\leq 1.5 cm in their greatest transverse diameter for nodes > 1.5 cm before therapy). Previously involved nodes that were 1.1 to 1.5 cm in their greatest transverse diameter before treatment must have decreased to \leq 1 cm in their greatest transverse after treatment or by more than 75% in the sum of the products of the greatest diameters. The spleen, if consider to be enlarged before therapy on the basis of a CT scan must have regressed in size and must not be palpable on physical examination. Any macroscopic nodules in any organs detectable on imaging techniques should no longer be present.
- 11.3.2 Complete response unconfirmed (CRu): A residual lymph node mass > 1.5 cm in greatest transverse diameter that has regressed by > 75% in sum of the products of the greatest diameters, does not change over the last two treatments, has a negative PET scan, and any biopsies obtained are negative will be considered to be in CR. In organs involved by disease, any residual lesions that have decreased by > 75% in sum of the products of the greatest diameters or are < 1 cm, are consistent with scar, and stable over the last two treatments will be considered to fulfill criteria for CR.
- 11.3.3 Partial response (PR): 50% or greater decrease in the sum of the products of the longest perpendicular diameters of all measured lesions lasting for a period of at least one month. No individual lesions may increase in size and no new lesions may appear.

•Patients in PR with an estimated >80% reduction in initial tumor bulk whose measurable disease does not change between cycles 4 and 6, and have a negative PET scan after cycles 4 or 6 will be considered to be in clinical CR.

- 11.3.4 Stable disease (SD): Tumor measurements not meeting the criteria of CR, PR, or PD.
- 11.3.5 Progression (PD): Increase of 25% or more in the sum of the products of the longest perpendicular diameters of all measured lesions compared to the smallest previous measurements, or the appearance of any new lesion(s).

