3. PATIENT SELECTION

3.1 Eligibility Criteria

- 3.1.1 Patients must have histologically documented metastatic solid tumors which have progressed after one line of therapy, or lymphoma which has progressed after initial therapy and without potentially curative options, or patient refuses potentially curative therapy.
- 3.1.2 Patients must have measurable or evaluable disease.
- 3.1.3 Age ≥ 18 years.
- 3.1.4 ECOG performance status ≤ 2 (see Appendix A).
- 3.1.5 Life expectancy of greater than 3 months.
- 3.1.6 Patients must have normal organ and marrow function as defined below:

| _ | leukocytes | ≥3,000/mcL |
|---|---------------------------|--|
| _ | absolute neutrophil count | ≥1,500/mcL |
| _ | platelets | ≥100,000/mcL |
| _ | total bilirubin | within normal institutional limits |
| _ | AST(SGOT)/ALT(SGPT) | $\leq 2.5 \times \text{institutional upper limit of normal (ULN)}$ |
| _ | serum creatinine | $\leq 1.5 \times \text{institutional ULN}$ |
| | | OR |
| - | creatinine clearance | \geq 60 mL/min/1.73 m ² for patients with serum creatinine levels >1.5 × higher than institutional normal |

3.1.7 Anticoagulation with low-molecular-weight heparin (LMWH) or any direct oral anticoagulant (DOAC, *e.g.*, rivaroxaban, apixaban, dabigatran, or edoxaban) will be permitted. Patients receiving treatment with warfarin will be given the option to switch to LMWH or a DOAC.

- 3.1.8 Patients must have recovered to grade 1 or baseline from adverse events (22) and/or toxicity of prior chemotherapy or biologic therapy. They must not have had chemotherapy, biologic therapy, or definitive radiotherapy within 4 weeks (6 weeks for nitrosoureas and mitomycin C) or 5 half-lives, whichever is shorter, prior to entering the study. Palliative-intent radiotherapy (30 Gy or less) must be completed at least 2 weeks prior to start of treatment, and may not be to a lesion that is included as measurable disease. Patients must be ≥2 weeks since any investigational agent administered as part of a Phase 0 study (where a sub-therapeutic dose of drug is administered) at the PI's discretion, and should have recovered to grade 1 or baseline from any toxicities.
- 3.1.9 Patients receiving denosumab or bisphosphonates for any cancer, or undergoing androgen deprivation therapy for prostate cancer, are eligible for this therapy.
- 3.1.10 Prior therapy with topoisomerase I inhibitors is allowed.

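### The lymphoma progression rule in 11.3.5 omits growth of existing unmeasured disease, and it can label a small residual node as progression while the node is still of complete-response size

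*Combined protocol and SAP*

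**What the plan says.** All references are to the combined protocol and SAP.

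- **Lymphoma PD (11.3.5).** The first trigger is "Increase of 25% or more in the sum of the products of the longest perpendicular diameters of all measured lesions", taken against the smallest earlier measurements. The second is any new lesion. There is no third trigger, no minimum absolute increase and no minimum node size.
- **Lymphoma stable disease (11.3.4).** This is the residual category: "Tumor measurements not meeting the criteria of CR, PR, or PD".
- **Lymphoma complete response (11.3.1).** "All lymph nodes and nodal masses must have regressed to normal size". For larger nodes the limit is at most "1.5 cm in their greatest transverse diameter for nodes > 1.5 cm before therapy". Nodes of 1.1 to 1.5 cm before treatment must fall to 1 cm or less, or shrink by more than 75% in the sum of products. The section also asks for an enlarged spleen to regress.
- **Lymphoma partial response (11.3.3).** Growth of any one lesion rules out partial response, but nothing in 11.3 turns that growth into PD.
- **Solid tumors (11.2.4.1, 11.2.4.2).** These rules contain both elements that 11.3.5 lacks: an absolute minimum of 5 mm on the sum of diameters, and a non-target rule, "Appearance of one or more new lesions and/or unequivocal progression of existing non-target lesions". Section 11.3 does not refer to either.
- **Eligibility (3.1.2).** "Patients must have measurable or evaluable disease".
- **Use of PD (5.4).** Disease progression is one of the criteria that end treatment.

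**The concern.** The two gaps push classification in opposite directions.

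Leaving out existing unmeasured disease makes results look too good. A patient whose spleen or effusion clearly worsens while the measured nodes hold steady is counted as stable. The protocol treats the spleen as relevant to complete response but gives it no role in progression.

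A purely relative threshold taken from the nadir makes some results look too bad. The smaller the residual node, the fewer millimetres are needed, so good responders are the most exposed to PD by measurement noise. A scan can also meet the nodal size limit for complete response and the PD rule together, and no precedence is stated.

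At stake are best response, duration of response or stable disease, and time on treatment for lymphoma patients. Lymphoma is part of the study population, and the dog lymphoma data are part of the stated rationale (2.5).

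**Working it through.** The plan gives no figure of its own that depends on this rule, so there is none to reproduce.

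**Inputs.** PD ratio 1.25 on the sum of products against the nadir (11.3.5). Complete-response node limits 15 mm and 10 mm (11.3.1). Restaging every 2 cycles (5 and 11.2). Reader error is not given anywhere; I assume independent normal error with a standard deviation of 0.5, 1.0 or 1.5 mm per diameter.

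**Step 1. Existing unmeasured disease, rules side by side**

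| Situation | Solid tumors (11.2.4) | Lymphoma (11.3) |
|---|---|---|
| Measured lesions stable, existing unmeasured sites clearly grow, nothing new | PD | Not PD; stable disease under 11.3.4 |
| No measured lesion, existing disease clearly grows, nothing new | PD | No sum of products exists, so the 25% trigger cannot operate; stable by default or unclassified |
| New lesion | PD | PD |

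**Step 2. Growth needed for PD**

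Both diameters growing in proportion: factor = sqrt(1.25) = 1.118, so +11.8% each.

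| Nadir diameter (mm) | PD reached at (mm) | Growth (mm) |
|---|---|---|
| 8.94 | 10.0 | 1.06 |
| 10 | 11.18 | 1.18 |
| 12 | 13.42 | 1.42 |
| 13.42 | 15.0 | 1.58 |

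Growth of 1 to 2 mm corresponds to nadir diameters of 1/0.118 = 8.5 mm to 2/0.118 = 16.9 mm. The largest nadir that still ends within the 15 mm limit is 15/1.118 = 13.4 mm.

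Example: a node at 12 x 10 = 120 mm² grows to 13.5 x 11.2 = 151.2 mm². The ratio is 151.2/120 = 1.26. That is PD, with the longest diameter still under 15 mm.

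Only one diameter growing: +25% is needed, so 10 to 12.5 mm (+2.5) or 12 to 15 mm (+3.0).

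Several nodes: if only one of n equal 13 mm nodes grows, its product must rise by the factor 1 + 0.25n, so the growth needed is 13 x (sqrt(1 + 0.25n) - 1).

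- n = 1: +1.5 mm, ending at 14.5 mm
- n = 2: +2.9 mm, ending at 15.9 mm
- n = 3: +4.2 mm, ending at 17.2 mm

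From n = 2 the growing node is above 15 mm, and the overlap with complete-response size is gone.

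**Step 3. Chance of false PD with no true change**

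Monte Carlo, 200,000 runs. PD is called if the sum of products is at least 1.25 times the smallest earlier sum. Four follow-up scans correspond to 4 x 2 = 8 cycles.

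| Measured disease (unchanged) | Assumed reader standard deviation | 1 scan | Within 2 | Within 4 |
|---|---|---|---|---|
| One 12 x 10 mm node | 0.5 mm | 1% | 2% | 6% |
| One 12 x 10 mm node | 1.0 mm | 11% | 27% | 55% |
| One 12 x 10 mm node | 1.5 mm | 21% | 45% | 78% |
| Two 12 x 10 mm nodes | 1.0 mm | - | - | 27% |
| Three 12 x 10 mm nodes | 1.0 mm | 2% | 5% | 13% |
| One 12 x 10 mm node plus one 25 x 20 mm lesion | 1.0 mm | - | - | 3% |

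**Step 4. Does the 5 mm condition transfer?**

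In 11.2.4.1 it is "the sum must also demonstrate an absolute increase of at least 5 mm (0.5 cm"), a condition on a sum of diameters. If it were read as 5 mm on the longest diameter, a 12 mm node would have to reach 17 mm. With proportional growth the product then rises by (17/12)² - 1 = 101%, not 25%. The condition cannot be copied into a rule built on products without deciding what it applies to.

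**The case against.** The strongest case against runs as follows. Different progression rules for different diseases are not in themselves a contradiction. Antitumor activity is exploratory and is reported without formal adjustment (13.3). The MTD rests on cycle-1 DLTs and has already been identified (5.1.2.2). The number of lymphoma patients is unknown. All of this stands, and it limits the reach of the point. It does not remove the gaps, because nothing in 11.3 sends the reader to 11.2.4 or leaves progression to judgment.

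A reader might infer more than the documents support:

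- **That any 1-2 mm change is PD.** This needs growth in both diameters (or in a short axis of about 8 mm or less), and a sole or dominant node or joint growth of all measured nodes.
- **That about half of lymphoma responders would be falsely called PD.** The 55% belongs to one small sole node, an assumed 1 mm error and four scans. It falls to about 3% once a 25 x 20 mm lesion is in the sum.
- **That a patient can be in full complete response and PD at once.** Only the nodal size limit overlaps. Section 11.3.1 also requires all signs and symptoms to be gone for at least a month.
- **That every evaluable-only patient is credited with stable disease.** Section 11.3.4 speaks of measurements, so such a patient may instead be unclassified. Section 11.3 sets no cap on measured lesions, so how much disease stays unmeasured depends on practice.
- **That the CTC and ctDNA samples at progression are mislabelled.** The worksheet in Appendix C leaves the CTC draw at progression to the PI, and 9.2.3.1 links ctDNA analysis to restaging scans that suggest growth. Neither is tied to 11.3.5.
- **That the 5 mm solid-tumor minimum should simply be carried over.** It is on a different scale (Step 4).

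**Conclusion.** The concern holds in a limited form. The gap for unmeasured disease follows from the text alone and needs no assumption. The overlap between complete-response node size and PD also follows from the text, but only for nadir diameters up to about 13.4 mm when both diameters grow (12 mm when one grows), in a sole or dominant node or when all measured nodes grow together.

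How often noise would trigger PD is illustrative. For a single 12 x 10 mm node over four scans it ranges from 6% to 78% across assumed reader standard deviations of 0.5 to 1.5 mm.

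The effect is confined to exploratory best response, duration of response or stable disease, and time on treatment in lymphoma patients. Section 11.3 defines no duration of its own, so any effect there assumes that the definitions in 11.2.5 are used. MTD and DLT conclusions are unaffected. The correction is worth making because it is cheap and because the rule as written misclassifies, rather than merely lacking detail.

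**What to change.** Reconcile 11.3.1, 11.3.4 and 11.3.5 with each other and with 11.2.4.1-11.2.4.2, so that:

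1. response classification in lymphoma covers unequivocal growth of existing unmeasured disease, and says how evaluable-only patients are classified; and
2. the same scan cannot meet both the nodal size limit for complete response and PD, or a precedence is stated.

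Whether to set an absolute minimum, and at what value, is for the sponsor to decide. It should be expressed on the scale that 11.3.5 uses. Because PD also ends treatment under 5.4, the sponsor should say whether the reconciled wording applies there too; this review proposes no threshold for that purpose.

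Apply the reconciled criteria to the exploratory response analysis, using scans already taken.

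The cost is a protocol wording change and reclassification of the lymphoma patients already assessed, with no new procedures. The downside is that a true small-volume regrowth may be classified one restaging later.
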